### **2.3.1 Deferment Criteria (Prior to Vaccination of Doses 2 through 4)**

NOTE: SPONSOR must be notified of deferment. At sites located in the United States, site personnel should contact one of the study personnel listed on the Sponsor Contact page in the Administrative Binder. Internationally, the site should contact the local Merck subsidiary monitor.

1. The patient has an acute illness that requires active medical intervention or monitoring to avert serious danger to the participant's health or well-being and, in the opinion of the investigator, may interfere with the evaluation of the study objectives. (The maximum amount of time for which the vaccination should be deferred is 30 additional days).

2. The patient has received an inactivated vaccine such as the influenza vaccine. In that case, administration of the study vaccination should be deferred for 7 days following receipt of the inactivated vaccine.

The deferment criteria noted above must be reviewed prior to each vaccination for Doses 2 through 4, to ensure that patients do not meet the criteria specified. If a participant meets any deferment criterion, this must be reported to the SPONSOR, and all study procedures with the exception of the administration of the vaccine/placebo should be conducted on the day the vaccination was deferred.

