#### **Phase I Study Results in HM and STM Patients**

2. In the Phase I study, Protocol 002, 3 doses of vaccine induced a robust immune response in patients receiving chemotherapy for STM. A small increment in response was shown postdose 4 as indicated measured by IFN- $\gamma$  ELISPOT or gpELISA [16], which suggests additional benefit of further immunization. A similar kinetics of T cell response was noted in the HM population, even though the overall magnitude of the response was lower in that population. There is a possibility that the increase in immune response following the fourth vaccine dose could confer a true advantage in efficacy (as it does in auto-HCT patients) or duration or protection in STM and HM patients. However, a direct demonstration would require clinical efficacy studies that assess different dose regimens, as was done for the auto-HCT group to establish POC. Such studies are not feasible for the HM and STM populations because of the very large number of patients that would be required.
3. In the Phase I study, Protocol 002, the postdose 4 responses measured by IFN- $\gamma$  ELISPOT GMC were generally of comparable magnitude in the auto-HCT and STM groups. At postdose 3, responses were higher in the STM group than in the autologous HCT group. However, the postdose 3 response for STM patients was not as high as the postdose 4 response for auto-HCT patients. These findings raise the possibility that, as was demonstrated in the POC studies for autologous HCT, 3 doses of vaccine may not provide sufficient protection in STM patients.

4. The IFN- $\gamma$  ELISPOT GMC observed postdose 3 and postdose 4 for the HM group was substantial since the fold rise in GMC was comparable to that seen for older subjects in the ZOSTAVAXTM pivotal study. However, it was lower than for either the autologous HCT or STM groups. Therefore, a 3-dose regimen may not provide sufficient protection in HM patients, and a 4-dose regimen may be an appropriate choice in HM patients to further enhance immune responses and establish protective immunity.

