### 3.5.5.1.1 Analysis of Vaccine Efficacy on Incidence of HZ Cases

The primary efficacy endpoint is the incidence of HZ in the vaccine and placebo groups in the STM population, defined as the number of HZ cases per 1000 person-years of follow-up from study enrollment to the end of study. Vaccine efficacy for HZ ( $VE_{HZ}$ ) is defined as the relative reduction of the hazard rate of HZ in the V212 group compared with that in the placebo group in STM population. The primary statistical hypothesis for the primary efficacy is  $H_0: VE_{HZ} \leq 25\%$  versus  $H_1: VE_{HZ} > 25\%$ .

To address the primary hypothesis, a Cox proportional hazards regression model in VZV vaccine and placebo recipients stratified by age (< 50 years of age versus  $\geq 50$  years of age based on a MITT population as described in section 3.5.4.1) will be used as the primary analysis to compare the incidence of HZ between the vaccine and placebo groups. The study time period in the primary analysis will be from the enrollment to the stop date of HZ surveillance. Patients who do not develop HZ will be censored at the stop date of HZ surveillance. The follow-up time for patients who develop HZ will be from the enrollment to their HZ onset date. For the interim analysis, this stop date will be the corresponding database cutoff date for the analysis. Efron's method will be used to handle ties in event times.

A key supportive analysis will include calculation of  $VE_{HZ}$  using a PP population as described in section 3.5.4.1 based on Cox proportional hazards regression model. The study time period in the primary analysis will be from the date of Dose 4 to the stop date of HZ surveillance. The model and covariate adjustment will be similar to that noted in the MITT approach. In addition, incidence of HZ and  $VE_{HZ}$  will also be summarized by age group (50 to 59, 60 to 69, and 70+) as exploratory analyses.

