The results of HZ case determination (PCR versus case adjudication by the CAC) will be summarized by vaccination group. The probability of developing HZ will be estimated and displayed by the Kaplan-Meier method. The incidence rates of HZ post randomization (enrollment) in each group will be compared by the nonparametric log-rank statistic without covariate adjustment. Also, the incidence of HZ will be summarized by vaccination group in terms of number of cases per 1000 person-years in those patients who only received a total of 1 dose, 2 doses, and 3 doses of vaccine/placebo using the MITT population if a sizable proportion (>10%) is observed in each category (1 dose, 2 doses, and 3 doses).

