### 3.5.5.1.5 Additional Evaluation of Vaccine Efficacy

To further evaluate the vaccine efficacy for HZ, summaries for the incidence of HZ, secondary composite endpoint and PHN in each vaccination group will also be provided by the following subgroups:

- Disease type and HM immunocompromise category (STM, HM low IC or HM moderate to high IC).
- Gender (male versus female)
- Number of vaccine doses received
- Age categories (< 50 years, 50 to 69, and 70+)

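### HZ incidence by number of doses received groups patients by final dose count but counts from enrollment, so it can show a spurious dose gradient if some early HZ ends vaccination

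*Combined protocol and SAP*

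**What the plan says.** Section 3.5.5.1.1 summarizes HZ cases per 1000 person-years by vaccination group "in those patients who only received a total of 1 dose, 2 doses, and 3 doses of vaccine/placebo using the MITT population", but only "if a sizable proportion (>10%) is observed in each category (1 dose, 2 doses, and 3 doses"). Section 3.5.5.1.5 lists "Number of vaccine doses received" among the subgroups for HZ, the composite endpoint and PHN. It sets no threshold there, and it is the only source of a 4-dose rate.

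Neither place gives a time origin of its own. The one defined for the primary endpoint is enrollment: the endpoint is the "number of HZ cases per 1000 person-years of follow-up from study enrollment to the end of study", and for cases, "The follow-up time for patients who develop HZ will be from the enrollment to their HZ onset date". MITT (3.5.4.1) requires one dose, with no landmark and no HZ-free condition.

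The plan takes more care elsewhere. The per-protocol analysis starts its clock at Dose 4 and excludes patients with HZ up to 28 days after Dose 4. Section 3.5.5.1.2 warns that the comparison of PHN among HZ cases lacks the protection of randomization. The dose-count summaries carry neither safeguard.

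HZ is not among the reasons in 2.3.2 for withholding further doses. For acute illness, 2.3.1 provides deferral: "The maximum amount of time for which the vaccination should be deferred is 30 additional days". What happens to later doses after HZ between doses is not stated.

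**The concern.** Final dose count becomes known about three months after time zero on the planned schedule, yet events before then are counted. This has two separate consequences.

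- **Reverse causation.** If HZ after Dose 1 leads to no further doses, the patient is in the 1-dose group because of the event, and the 4-dose group is cleared of that case. This needs some HZ to end vaccination.
- **Misattribution.** HZ 15 days after Dose 1 in a patient who later completes is a 4-dose case, and about 90 days before Dose 4 count as 4-dose time. This needs no assumption about stopping.

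Section 3.1.2.2 leaves open whether the fourth dose matters: "There is a possibility that the increase in immune response following the fourth vaccine dose could confer a true advantage in efficacy". It adds that a direct demonstration is not feasible. These summaries are the only planned efficacy output on partial regimens, and reverse causation would make four doses look better than fewer.

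**Working it through.** **The plan's own figure.** The documents give none for the dose-count summaries. The nearest is the primary power in 3.5.7.1: 90 cases, one-sided 0.0125, VE 65% against 25%. Conditional on the case split, p0 = 0.75/1.75 = 0.4286 and p1 = 0.35/1.35 = 0.2593. Success requires at most 27 vaccine cases, and P(X ≤ 27) at p1 is 84.2%, as stated. Only the split by randomized arm enters, so dose count cannot affect it.

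**Inputs from the documents.** Placebo rate 17 per 1000, taken as per person-year, and 1348 STM placebo patients (3.5.7.1). Doses about 30 days apart (3.2.1). A 36-month enrollment within about 5 years gives 2 to 5 years of follow-up, midpoint 3.5.

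**Assumptions not in the documents.** Constant hazard. q, the probability that HZ before the next dose permanently ends vaccination, from 0 to 1. Stopping for other reasons of 12/12/14% before Doses 2/3/4, chosen to pass the 10% rule, or 5% per interval. At 12/12/14% and q=0 the groups hold 162, 142 and 146 of 1348 (12.0%, 10.5%, 10.8%).

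**1-dose group, placebo, 12/12/14%, all followed 3.5 years.**

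- HZ in the first 30 days (0.082 year): 1348 × (1 − exp(−0.017 × 0.0821)) = 1.881.
- Stopping for other reasons: 0.12 × (1348 − 1.881) = 161.5.
- Their later cases: 161.5 × (1 − exp(−0.017 × 3.418)) = 9.118.
- Person-years: 161.5 × 0.0821 + 9.118/0.017 = 549.6.
- Early cases falling in this group: 1.881 × [q + 0.12(1 − q)].
- Rate at q=0: (9.118 + 0.226)/549.6 = 17.0. At q=0.5: (9.118 + 0.940 + 0.113)/549.7 = 18.5. At q=1: (9.118 + 1.881)/549.7 = 20.0.

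**4-dose group.** At q=1, 894.0 HZ-free patients reach Dose 4. They have 894.0 × (1 − exp(−0.017 × 3.254)) = 48.1 cases over 894.0 × 0.2464 + 48.1/0.017 = 3050 person-years, a rate of 15.8. At q=0, another 3.75 patients with earlier HZ complete the course: 51.86/3050.5 = 17.0. So with no stopping at all, 3.75/51.86 = 7% of the placebo 4-dose cases arose before Dose 4.

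**Results per 1000 person-years; the true value is 17.0 throughout. Completers are followed 3.5 years.**

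| Other stopping | Other stoppers followed | q | 1 dose | 2 doses | 3 doses | 4 doses |
|---|---|---|---|---|---|---|
| 12/12/14% | 3.5 y | 0 | 17.0 | 17.0 | 17.0 | 17.0 |
| 12/12/14% | 3.5 y | 0.25 | 17.8 | 17.6 | 17.4 | 16.7 |
| 12/12/14% | 3.5 y | 0.5 | 18.5 | 18.3 | 17.8 | 16.4 |
| 12/12/14% | 3.5 y | 1 | 20.0 | 19.6 | 18.7 | 15.8 |
| 12/12/14% | 1 y | 1 | 27.3 | 25.9 | 22.8 | 15.8 |
| 5% each | 3.5 y | 0.5 | 20.9 | 20.7 | 20.5 | 16.4 |
| 5% each | 3.5 y | 1 | 24.8 | 24.4 | 23.9 | 15.8 |

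Simulation with 2 to 5 years of follow-up and 10% yearly loss gives slightly larger shifts: 20.7/19.9/19.1/15.6 at q=1 with 12/12/14%, and 22.1/21.4/21.1/16.3 (q=0.5) and 26.2/25.9/25.2/15.5 (q=1) with 5%. At 5% no category exceeds 10%, so only 3.5.5.1.5 would report those rates.

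Assigning person-time to doses already received returns about 17 in every dose interval, whatever q is.

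**The case against.** The strongest reply is that the mechanism is not in the documents. HZ is not a listed reason to stop vaccination, acute illness leads to deferral, and 3.2.1 handles missed windows by consultation. The per-protocol definition requires four doses and, separately, no early HZ, so it contemplates four-dose recipients with earlier HZ. This stands: q is unknown and the bias is zero at q=0. Some stopping is still plausible. Suspected HZ triggers prompt antiviral treatment (3.2.17.5) and review every 3 to 5 days (3.2.17.3), deferral is capped, and 3.2.20 lets investigators withdraw patients for untoward effects.

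A reader might infer that the summary, as written, must show a dose gradient and so support four doses by artefact. The documents do not support that: it can do so, but only if q exceeds zero. Nor does misattribution point that way. It creates no placebo gradient under a constant hazard, and in the vaccine arm it would make four doses look worse if protection builds with dosing. A reader might also arrive at a 1-dose rate near 70 per 1000. That needs q=1, 5% stopping and other stoppers followed only half a year, whereas 3.2.19 asks for at least one year after the last vaccination.

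Two further points stand. The outputs are descriptive and shown by arm, so a placebo gradient would be visible. And the shift is small against noise: 10 cases over 162 × 3.5 = 567 person-years have exact 95% limits of 4.80 and 18.39 cases, or 8.5 to 32 per 1000, so 17 and 18.5 cannot be told apart.

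Dose-interval person-time also ties dose count to time since enrollment. Section 3.1.1.2 reports higher HZ risk on current chemotherapy, so if risk falls later, rates across intervals would differ even on placebo. That limits how the fix may be read; it does not justify the current grouping.

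**Conclusion.** The concern holds as a conditional weakness of two descriptive summaries. Grouping by final dose count with a clock from enrollment inflates the 1- to 3-dose rates and deflates the 4-dose rate, in both arms, whenever some HZ before Dose 4 ends vaccination.

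At stopping levels that trigger the 3.5.5.1.1 summary, with all patients followed 3.5 years, the apparent placebo advantage of four doses over one is 1 − 16.7/17.8 = 6% at q=0.25, 11% at q=0.5 and 21% at q=1. It reaches 1 − 15.8/27.3 = 42% at q=1 if other stoppers are followed one year. The 4-dose rate itself falls by at most about 7 to 9% (15.8 to 15.5 against 17). These sizes rest on the assumed q, stopping rates and constant hazard.

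Independently of q, HZ before Dose 4 in completers is credited to four doses, and the two sections disagree on when the output is produced. A reader might infer that the efficacy claim is at risk. It is not: the primary MITT Cox analysis compares randomized arms and does not use dose count.

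**What to change.** In 3.5.5.1.1 and 3.5.5.1.5, replace grouping by total doses with dose-interval person-time:

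- Assign each MITT patient's HZ case and person-years to the number of doses received before onset: after Dose 1 and before Dose 2, after Dose 2 and before Dose 3, after Dose 3 and before Dose 4, after Dose 4. A patient who stops stays in the last interval reached.
- Report vaccine against placebo within each interval. Do not compare rates across intervals, because dose count is tied to time since enrollment.
- State the time origin, and label the result descriptive and not protected by randomization, as 3.5.5.1.2 already does for PHN among HZ cases.
- Use one reporting trigger in both sections.

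The cost is SAP wording and minor programming, since 3.2.14.1 already has all vaccinations recorded. The downside is sparse early intervals: about 1.9 placebo cases per 30 days, or 5.6 over the first 90 days, among 1348 patients.

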### 3.5.5.1.2 Analysis of Vaccine Efficacy on Secondary Efficacy Endpoints

Three secondary efficacy endpoints are defined for the STM population and in the HM population on an exploratory basis.

Since the incidences of moderate to severe HZ-associated pain, HZ-complications as defined by the composite endpoint, and PHN are unknown in this population, formal hypothesis testing for these secondary endpoints will not be performed. The incidence of the secondary efficacy endpoints of moderate to severe HZ-associated pain, composite complication endpoint, and the incidence of PHN, defined as pain in the area of the HZ rash with a “worst pain in the last 24 hours” score of 3 or greater (on a 0 to 10 scale) on the ZBPI that persists or appears greater than or equal to 90 days after HZ onset, (point estimate and 95% CI) will be compared between vaccine and placebo groups using Cox proportional hazards regression stratified by age (< 50 years of age versus  $\geq$  50 years of age) based on the MITT population. For patients who develop PHN, the PHN event onset will be the date of HZ rash onset. Patients who do not develop PHN will be considered as censored at the stop date of their HZ surveillance. Furthermore, the count and proportion of each component of the secondary efficacy composite endpoint among all randomized patients in the vaccine and placebo groups will be summarized.

Sensitivity analyses for vaccine efficacy on PHN based on alternative definitions [pain in the area of the HZ rash with a “worst pain in the last 24 hours” score of 3 or greater (on a 0 to 10 scale) on the ZBPI that persists or appears more than 30, 60, 120, and 180 days after HZ rash onset] will be compared between the vaccine and placebo groups in the MITT population.

To evaluate the vaccine effect on PHN above and beyond that on HZ incidence, the proportions of patients who develop PHN among HZ cases will be provided by vaccination group. A generalized linear regression model with log-link will be used to estimate the relative risk reduction of PHN among HZ cases in vaccine recipients compared with placebo recipients. This model will include incidence of PHN as a binary response variable, and include vaccination group, and age as covariates. An exploratory analysis will be performed using the similar model, with the use of antiviral drug initiated within 72 hours of HZ rash onset (Yes versus No) added as an additional covariate. Note that these analyses are not protected by randomization, and with the post-randomization variable, antiviral use in the model, the results might be subject to potential bias.

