### 1.2 INDICATION

The proposed indication for V212/inactivated varicella-zoster virus (VZV) vaccine is the prevention of herpes zoster (HZ) and HZ-related complications in immunocompromised patients with solid tumor malignancy (STM).

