### 3.1.1.2 Epidemiology of HZ in Patients with STM

Published data of HZ in the STM patient population are much more limited than for other IC populations. HZ incidence in this population was reported to range from 12 to 15 per 1000 person-years [33-39]. Aggressive and prolonged chemotherapy was widely identified as the primary factor for VZV reactivation [33-39]. In the KPNC study, the incidence of HZ among ~12,000 STM patients diagnosed during the study time period was 12 per 1000 person-years [13]. The incidence was 19, 20, and 10 per 1000 person-years in the high, moderate, and low IC groups respectively. The incidence of HZ among patients with breast, prostate, lung and bronchus, colon and melanoma cancer was 15, 10, 21, 8, and 9 per 1000 person-years respectively. When compared with the general population, adjusting for age and gender, STM patients in general had ~2-fold increased risk of the general population while patients currently on chemotherapy or corticosteroid therapy had ~3 fold increased risk. Complications of HZ can be a significant burden to the STM patient. The proportion of HZ cases with PHN was estimated to be as frequently as 8% to 42% [13, 35, 36]. Among the HZ cases in STM patients in the KPNC study, it was shown that ~23% had at least one complication (PHN or any non-pain related complications) [13]. PHN (defined as zoster-associated pain persisting or appearing at or beyond 90 days post-HZ onset) occurred in 8.6% of the patients. Multiple dermatome involvement, skin-related, eye related, and neurological complications occurred in 8.5%, 7.7%, 3.2%, and 0.4% of HZ cases respectively.

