### 3.5.6 Multiplicity

With the decision made from the first interim futility analysis (provided in Sections 1.3 and 1.4), there is only one efficacy analysis performed for the primary efficacy hypothesis in the STM population. As no population enrichment is planned, no multiplicity adjustment will be made for primary efficacy analysis in the STM population and the primary efficacy hypothesis will be tested at one sided  $\alpha=0.0125$ .

No multiplicity adjustment will be made for the analyses related to the secondary objective and exploratory objectives, including any analyses related to immunogenicity, due to their exploratory nature.

For comparisons of adverse experiences between the vaccine and placebo groups, the goal is to investigate if there exists an overall trend of risk difference between the 2 groups. It is recognized that there exists a multiplicity issue for conducting multiple comparisons on these items, with each comparison being performed at the two-sided 0.05 level (corresponding to the 95% CI). Since the overall significance level for these comparisons will be much  $>0.05$ , caution should be exercised when interpreting the results.

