### 3.5.7 Sample Size and Power

#### 3.5.7.1 Efficacy Analysis

This is an event-driven study. With a 1:1 randomization ratio between the vaccine and placebo groups and a total of 90 HZ cases in the STM population with 2696 patients, the study will have an overall power of ~84.2% to detect 65%  $VE_{HZ}$  at the overall two-sided 0.025 significance level, based on the success criterion of the lower bound 97.5% CI for  $VE_{HZ}$  being greater than 25%. Table 3-3 also provides power for a variety of assumed vaccine efficacy.

Table 3- 3 Power for Primary Efficacy in the STM Population with 90 Cases

Cases	Power at assumed vaccine efficacy (VE)					
	VE=80	VE=75	VE=70	VE=65	VE=60	VE=55
90	99.9%	99.2%	95.0%	84.2%	66.6%	46.7%

To accrue ~90 confirmed HZ cases in the STM population during the time period from enrollment through approximately the end of maximum 5 years postvaccination, enrollment of approximately 2696 patients (1348 receiving vaccine and 1348 receiving placebo) will be required, assuming 1) 30% total lost-to-follow-up, 2) an HZ rate of 17 per 1000 in the placebo group, 3)  $VE_{HZ}=65\%$ , and 4) 36 months of study enrollment. The sample size calculation follows the methods described in Lachin [21].

The dropout rates and the HZ event rates will be monitored on an ongoing basis using the blinded database. If the observed HZ case accrual rate indicates that more than 5 years of patient follow-up will be necessary to accrue the targeted number of confirmed cases, then the SPONSOR will consider it beyond the adjustment cap and terminate the study without extended follow-up time and increasing enrollment. Because of the event driven design, no additional interim analysis is expected to be performed when follow-up time is extended or when enrollment is increased. Should enrollment increase, patients enrolled under this scenario will also be followed for safety and efficacy for at least 1 year following receipt of their last dose of V212 or placebo.

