Since the incidence of clinically significant pain, complications as defined by the composite secondary endpoint and PHN are unknown in this population, formal hypothesis testing for these secondary endpoints will not be performed, but rather the analysis will focus on the estimation of the vaccine efficacy on these endpoints. To quantify the precision of the analysis, as an example, if the underlying true vaccine efficacy for any one of these secondary endpoints is 52%, and 10% of HZ cases developed a secondary endpoint for vaccine and placebo group, then at interim and final analysis where the HZ case split between vaccine and placebo has met the statistical success criterion for the primary hypothesis, the point estimates and CIs (adjusting for multiplicity) on the secondary endpoints efficacy are roughly 50% (-80%, 88%) and 40% (-50%, 77%), respectively. If 20% of HZ cases developed a secondary endpoint, then the above point estimates and CIs are 48% (-24%, 80%) and 44% (-1%, 71%), respectively. If 40% of HZ cases developed a secondary endpoint, then the above point estimates and CIs are 48% (5%, 72%) and 43% (11%, 64%), respectively.

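### The proposed indication includes HZ-related complications, but pain, the complication composite and PHN get no error-controlled test, although one gated on primary success would cost no alpha

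*Combined protocol and SAP*

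**What the plan says.** - Section 1.2 gives the proposed indication as "prevention of herpes zoster (HZ) and HZ-related complications in immunocompromised patients with solid tumor malignancy (STM").
- Section 2.1.3 lists three secondary objectives, for STM only: moderate to severe HZ pain, a composite of HZ complications, and PHN. Exploratory objectives are listed separately in 2.1.4.
- Section 3.5.5.1.2 says that "formal hypothesis testing for these secondary endpoints will not be performed", because the incidences are unknown in this population. A Cox model stratified by age gives a VE estimate with a 95% CI in the MITT population.
- Section 3.5.7.1 repeats the exclusion: "but rather the analysis will focus on the estimation of the vaccine efficacy on these endpoints".
- Section 3.5.6 says: "No multiplicity adjustment will be made for the analyses related to the secondary objective and exploratory objectives". It calls these analyses exploratory.
- The one primary test in STM has the null VE ≤ 25% and is powered "at the overall two-sided 0.025 significance level", that is, one-sided 0.0125 (2.1.2, 3.5.6).

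No section links the secondary endpoints to the primary by a hierarchy or gate.

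**The concern.** The indication has two parts and the plan tests one. Whatever the data show on complications, the result will be an estimate with an unadjusted 95% CI. If readers treat the three secondary intervals as tests, the chance of at least one false positive is up to 1 − 0.975³ = 7.3% one-sided under independence. The endpoints are correlated, so the true figure is lower, but the plan does not control it.

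The reason given does not lead to the choice made. Not knowing how many HZ cases will have pain or complications means that power cannot be promised. A test carried out only after primary success, at the same level, holds its error rate at any incidence. At stake is whether a convincing result on pain or complications could be reported as a controlled finding.

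**Working it through.** **Inputs.** From 3.5.7.1: 90 HZ cases, 1:1 allocation, VE 65%, two-sided 0.025, null VE ≤ 25%, and an example VE of 52% for a secondary endpoint with 10%, 20% or 40% of HZ cases affected. From 3.1.1.2, for STM HZ cases in the cited cohort: about 23% with at least one complication and 8.6% with PHN. Assumed: a pain share of 40–50% (only 40% appears in the plan, as a generic scenario); equal shares in both arms among HZ cases, as in 3.5.7.1; similar person-time in the arms, so that the case split stands in for the Cox model.

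**Step 1: reproduce the plan's power.** Given 90 cases, the vaccine-arm count is binomial with probability (1 − VE)/(2 − VE).
- Under the null: 0.75/1.75 = 0.4286. P(X ≤ 27) = 0.0083 and P(X ≤ 28) = 0.0149, so success requires at most 27 vaccine cases.
- At VE 65%: 0.35/1.35 = 0.2593 and P(X ≤ 27) = 84.2%, the plan's figure. VE 80, 75, 70, 60 and 55% give 99.9, 99.2, 95.0, 66.6 and 46.7%, matching Table 3-3.

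**Step 2: alpha.** In a fixed sequence that stops at the first failure, a false claim requires rejecting the first true null in the order, which is tested at 0.0125. Simulated family-wise error is 0.0083 with the primary null true, and 0.0065–0.0086 with primary VE 65% and the first secondary null true. The primary rule is untouched.

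**Step 3: what each secondary test requires.** Null VE ≤ 0 means a vaccine share of 0.5, tested by exact binomial at one-sided 0.0125.

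| Endpoint (share of HZ cases) | Expected cases, 90 × share | Most vaccine cases allowed | Expected vaccine cases at VE 65% |
|---|---|---|---|
| Pain (40%) | 36 | 10 of 36 | 9.3 |
| Complications (23%) | 20.7 | 4 of 21 | 5.4 |
| Complications (10%) | 9 | 0 of 9 | 2.3 |
| PHN (8.6%) | 7.7 | 0 of 8 | 2.1 |

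Fewer than 7 cases can never reach significance: 0.5⁶ = 0.0156 is above 0.0125 and 0.5⁷ = 0.0078 is below it.

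**Step 4: power of the sequence primary → pain → complications → PHN.** Simulated, and joint with success at every earlier step. Overlap between endpoints is not given in the documents, so the ranges run from independent to fully nested and over pain shares of 40–50%.

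| Endpoint | VE 65% | VE 52% (HZ and secondaries) |
|---|---|---|
| Primary | 84% | 36% |
| Pain, 40–50% | 67–76% | 24–29% |
| Complications, 23% | 32–38% | 9–12% |
| Complications, 10% | about 10–11% | about 3% |
| PHN, 8.6% | 4–7% | 1–2% |

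Placed directly after the primary, complications would have 38% joint power at a 23% share and 12% at a 10% share (VE 65%). Pain would then pass only if complications did.

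**The case against.** Estimation only is an openly stated choice, and it is defensible with few expected events. The plan reports VE with a 95% CI, component counts and PHN sensitivity analyses, and it claims no confirmatory status for them. That stands: what is missing is a confirmatory statement, not an analysis.

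The better-powered endpoint is pain, which 2.1.3 separates from complications. For the complications themselves a formal test would more likely fail than succeed. That also stands, and it limits the gain. It does not argue against a test that costs the primary nothing.

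Three stronger readings are tempting, and the documents do not support them.
- *The claim of unknown incidence is contradicted by 3.1.1.2.* That section reports that "it was shown that ~23% had at least one complication (PHN or any non-pain related complications"). The figure counts PHN, and the section also itemises multiple-dermatome and skin events, which the trial composite does not name. Of the itemised categories only eye (3.2%) and neurological (0.4%) events clearly map to the composite. No rate is given for hospitalization, viremia, intravenous acyclovir or moderate to severe pain. Only PHN has a background figure, 8.6% in the cohort and 8% to 42% across sources, and it is not defined by the trial's ZBPI threshold.
- *A successful trial could support a label for HZ only.* No section says what evidence the indication requires, and 1.2 calls it proposed.
- *The change is only a matter of SAP wording.* Section 3.5 says that no separate SAP will be issued, so a protocol amendment is needed. It would follow the futility analysis of 29-Oct-2014, in which STM data were seen by the DMC and an unblinded sponsor statistician. Section 3.5.1 keeps study personnel blinded to the interim data, so this is no bar, but it should be documented.

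**Conclusion.** The concern holds as a gap between the proposed indication and what the plan allows the trial to conclude. Sections 3.5.5.1.2, 3.5.6 and 3.5.7.1 exclude any error-controlled test of the three secondary endpoints, and unknown incidence does not justify excluding a gated one.

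The gain lies mainly with a frequent endpoint, is modest for complications and is close to nil for PHN. The figures depend on the assumed pain share, on a 23% share borrowed from a differently defined cohort measure, on equal shares in the two arms and on VE 65%. Nothing here calls the primary test, its level or its power into question.

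**What to change.** Amend the protocol before final unblinding, in 3.5.5.1.2, 3.5.6 and 3.5.7.1:

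1. If the primary hypothesis is met, test H0: VE ≤ 0 in STM in a fixed order, each at one-sided 0.0125, stopping at the first failure. Put the endpoint expected to be most frequent first, for example moderate to severe pain, then the composite, then PHN.
2. Keep the 95% CIs and add the 97.5% CI that corresponds to each test.
3. Keep the statement that pain and composite incidences are unknown. Note only that 3.1.1.2 gives a background figure for PHN.
4. State power jointly with primary success, with its assumptions, including the low values for complications and PHN.
5. Recompute the precision example in 3.5.7.1. It still refers to an interim and a final analysis and to multiplicity-adjusted intervals, whereas 3.5.6 makes no adjustment. At the 27:63 boundary split, VE = 1 − 27/63 = 57%. With standard error √(1/(27s) + 1/(63s)) for log relative risk at share s, the 95% CIs are about (−78%, 90%), (−17%, 84%) and (13%, 79%) for s = 10%, 20% and 40%.

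Cost: one amendment after the interim futility look, with a note that study personnel were still blinded, and a likely non-significant formal result for the rarer endpoints. It needs no alpha, no patients and no change to the primary test.
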